7.2 Statistical Methods

The main analyses will focus on the monthly accrual rate (section 3.2). The number of patients accrued each month will be analyzed via Poisson regression. The mean (monthly rate) will be estimated and tested against the null value of 4 patients per month using a 1-sided test with alpha 0.05. In addition to accrual, we will also summarize the proportion of enrolled subjects who are lost to follow-up, since that could also impact the feasibility of the future randomized trial.

Additional analyses will focus on the secondary endpoints (section 3.3). For example, we will compute the average patient satisfaction score and test it against the null value of 75 using a one-sample t-test with alpha 0.05. We will also estimate the average patient rating of physician communication, patient distrust in the healthcare system, and physician satisfaction.

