KPS - Karnofsky Performance Status
PSCC – patient satisfaction with cancer care scale
CAT – communication assessment tool

Study Summary

Title	TELEPORT Study: A Pilot Feasibility Trial Examining The Use of Telehealth in Post Radiation Therapy Visits
Short Title	TELEPORT Study: Telehealth in Radiation Oncology
Protocol Number	15D.580
Phase	single arm pilot study
Methodology/Study Design	Any malignancy or benign condition treated with radiation single arm feasibility study
Study Duration	24 months for enrollment; 32 months for study duration
Study Center(s)	Single-center
Objectives	
Primary objective:
 
 - to investigate the feasibility of conducting a future phase 2 randomized study comparing telehealth and in person visits for patients returning for a post-radiation treatment visit 
Secondary objectives:
 
 - To examine patient satisfaction with a telehealth visit - To examine patient assessment of physician communication during a telehealth - To examine patient distrust in the healthcare system following a telehealth visit - To examine physician ability to perform a patient assessment during a telehealth visit - To examine physician perceptions of telehealth visits - To examine monetary and time cost to patients for telehealth visits - To calculate clinic savings derived from telehealth visits
Number of Subjects	65
Diagnosis and Main Inclusion Criteria	Patients receiving RT for any indication
Study Therapy,	Telehealth visit for the first post treatment follow up

Dose, Route, Regimen	
Duration of administration and follow-up	Follow up visit 3-8 weeks after completion of radiation treatment
Reference therapy	Standard in person office visit for first post treatment follow up
Statistical Methodology	

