7.0 STATISTICAL PLAN

7.1 Sample Size Determination

Accrual rate. This pilot study is designed to assess whether the accrual rate at Jefferson will be sufficient for a future noninferiority trial. For that noninferiority trial, we project that we will need to enroll a total of about 180 patients in three years, i.e., a minimum accrual rate of 5 patients per month. The enrollment duration of this pilot study will be 24 months. If the true accrual rate is 6 patients per month (i.e., 72 patients per year), then the pilot study has 83% power to establish that the accrual rate exceeds 5 patients per month (using a 1-sided test for Poisson rate, with alpha 0.05).

Patient satisfaction. The expected sample size of 60 patients will also have >90% power to establish that patient satisfaction will exceed 80%, assuming a true PSCC score of about 90% and a standard deviation of about 5% (using a one-sample t-test with alpha 0.05).

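### The primary accrual test uses a null of 4 patients per month, but the plan needs at least 5 and claims power against 5

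*Combined protocol and SAP*

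**What the plan says.** Section 3.2 makes rate of accrual the primary endpoint. Section 7.1 derives the benchmark from the planned randomized trial: "we will need to enroll a total of about 180 patients in three years, i.e., a minimum accrual rate of 5 patients per month". It then claims "83% power to establish that the accrual rate exceeds 5 patients per month", assuming a true rate of 6/month and a one-sided Poisson test at alpha 0.05, and states: "The enrollment duration of this pilot study will be 24 months".

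Section 7.2 describes the analysis. Monthly counts are modelled by Poisson regression, and the mean rate is "tested against the null value of 4 patients per month using a 1-sided test with alpha 0.05".

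On numbers, the Study Summary lists 65 under "Number of Subjects", and section 7.1 refers to "The expected sample size of 60 patients".

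**The concern.** Sections 7.1 and 7.2 describe the same one-sided test at the same alpha with different nulls. Rejecting 4/month shows only that the rate exceeds 4/month, and 4/month yields 4 × 36 = 144 patients in three years, not 180. The plan gives no reason for 4 and no separate go rule that brings the decision back to 5. The test could therefore read as success at a rate that section 7.1 regards as too low.

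Two neighbouring figures also affect the correction. The power stated in 7.1 has to be right for a null of 5, and the planned number of subjects has to be compatible with a test of a 24-month rate.

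**Working it through.** **Inputs.** Required rate 180/36 = 5/month, null 5, true rate 6/month, 24 months and one-sided alpha 0.05 (section 7.1). Null 4 (section 7.2). Subjects: 60 (section 7.1) or 65 (Study Summary).

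**Method.** For a null rate r0 over T months, the critical count c is the smallest with P(X ≥ c | r0·T) ≤ 0.05, where X is Poisson. The chance of a positive test at a true rate r is P(X ≥ c | r·T). This assumes that enrolment is not capped within the 24 months.

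**The plan's 83% first.**
- Null mean 5 × 24 = 120, so c = 139 (size 0.0482). True mean 6 × 24 = 144, and P(X ≥ 139 | 144) = 0.673.
- Score approximation: (144 − 120 − 1.645 × √120)/√144 = 0.498, which gives 0.69. The score, Wald, square-root and log approximations range from 0.64 to 0.71.
- Null 4 does not explain 83% either: power at a true 6/month over 24 months is 0.997.
- A 36-month duration comes close (exact 0.820, score 0.828), but section 7.1, section 3.1 and the Study Summary all give 24 months. At 24 months, 83% needs a true rate of about 6.26/month.

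**The two nulls over 24 months.**
- Null 4: mean 96, c = 113 (size 0.0489). The observed rate at the cutoff is 113/24 = 4.71/month, which projects to 4.71 × 36 = 169.5 patients (unrounded rate). The one-sided 95% lower bound there is 4.00/month.
- Null 5: c = 139, or 139/24 = 5.79/month.

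| True rate per month | Positive, null 4 | Positive, null 5 |
|---|---|---|
| 4.5 | 33% | 0.2% |
| 4.75 | 55% | 1.3% |
| 4.9 | 68% | 3% |
| 5 | 75% | 4.8% |
| 5.5 | 96% | 28% |
| 6 | 99.7% | 67% |

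A total of 113 to 138 patients passes the test in 7.2 and fails the criterion in 7.1. At exactly 5/month, where a claim that the rate exceeds 5 is false, the test in 7.2 is positive 75% of the time.

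**Delay to the future trial.** Time to 180 patients is 180/4.5 = 40.0 months or 180/4.9 = 36.7 months, against 36 planned.

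**Planned numbers.** 60/24 = 2.50/month and 65/24 = 2.71/month, both below either null. If enrolment stopped at 60 or 65 and the count were still divided by 24 months, neither null could be rejected.

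**If enrolment stopped at 65 and the time taken were tested** (an assumption, not in the plan). The time to the 65th patient is gamma with shape 65 and rate r.
- Null 4 is rejected at 13.08 months or less, that is 65/13.08 = 4.97/month or faster. Positive: 23% at a true 4.5/month, 47% at 4.9/month.
- Null 5 is rejected at 10.47 months or less (6.21/month). Positive: 0.8% at 4.5/month, 4% at 4.9/month. Power at 6/month is 41%.

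**The case against.** The strongest reply is that the practical harm is modest. The target is approximate, accrual of 4.5 to 4.9/month delays the future trial by only about 1 to 4 months, the estimated rate will be reported beside the test, and nothing makes rejection an automatic decision to proceed. All of that is fair. It limits the consequence but does not make the two sections agree.

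Second, the 33% and 68% figures require at least 113 patients, while the plan expects 60 or 65. On the time-to-65 reading, a positive test against 4 needs an observed rate of about 4.97/month, close to the minimum, and the chance of success at 4.5/month falls to 23%. This stands as a qualification. Even so, the chance at a true 4.9/month is 47% rather than 4%.

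Third, a null of 5 is demanding. At a true 5.5/month, which meets the minimum, the test is positive only 28% of the time over 24 months uncapped. The sponsor may prefer another decision rule, such as an explicit go rule or a confidence interval. That choice is open, but the plan does not make it, and section 7.1 as written claims to establish a rate above 5.

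Fourth, 67% is right only for uncapped 24-month enrolment and the exact test. That is correct, so the enrolment rule must be settled before the power figure is final.

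**Conclusion.** The concern holds and must be fixed. The only formal test of the primary endpoint uses a null below the plan's own minimum, so a positive result would not establish the rate the future trial needs. Under uncapped 24-month enrolment, the chance of a positive test at a true 4.5 to 4.9/month is 33% to 68%, against 0.2% to 3% with a null of 5. If enrolment stops at 65 and time is tested, it is 23% to 47% against 0.8% to 4%. The contradiction between the nulls depends on neither assumption. The stated 83% does not follow from its own inputs, and 60 or 65 subjects cannot support a positive test of a 24-month rate. Confidence is high.

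**What to change.** Make one joint edit to section 7.1, section 7.2 and the Study Summary.

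1. In 7.2, change the null from 4 to 5 patients per month.
2. Reconcile 60 and 65 subjects with the accrual test. State either that enrolment runs uncapped for 24 months (about 6 × 24 = 144 patients at the assumed rate), or that it stops at a fixed number and the time to reach it is tested.
3. In 7.1, replace 83% with the power for the chosen rule: about 67% for 24 months uncapped (exact Poisson, 5 versus 6, one-sided 0.05), or about 41% if enrolment stops at 65. Recompute it for any other rule.
4. In the same edit, check the satisfaction test. Section 7.1 powers it against 80%, while 7.2 will "test it against the null value of 75 using a one-sample t-test with alpha 0.05".

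The null and power corrections are text edits and need no new data items. The costs are a harder test and a lower stated power. Uncapped enrolment would also mean more subjects than the 65 now listed, each with a telehealth visit and surveys.

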7.3 Subject Population(s) for Analysis

All enrolled subjects will be analyzed. Subjects who withdraw or are lost to follow-up during the study will be counted in the accrual rate (since they will be part of the future randomized trial as per the intent-to-treat principle).

8.0 DATA HANDLING AND RECORD KEEPING

8.1 Confidentiality

Information about study subjects will be kept confidential and managed according to the requirements of the Health Insurance Portability and Accountability Act of 1996 (HIPAA). Those regulations require a signed subject authorization informing the subject of the following:

- What protected health information (PHI) will be collected from subjects in this study
- Who will have access to that information and why
- Who will use or disclose that information
- The rights of a research subject to revoke their authorization for use of their PHI.

In the event that a subject revokes authorization to collect or use PHI, the investigator, by regulation, retains the ability to use all information collected prior to the revocation of subject authorization. For subjects that have revoked

authorization to collect or use PHI, attempts should be made to obtain permission to collect at least vital status (i.e. that the subject is alive) at the end of their scheduled study period.

8.2 Source Documents

Source data is all information, original records of clinical findings, observations, or other activities in a clinical trial necessary for the reconstruction and evaluation of the trial. Source data are contained in source documents. Examples of these original documents, and data records include: hospital records, clinical and office charts, laboratory notes, memoranda, subjects' diaries or evaluation checklists, pharmacy dispensing records, recorded data from automated instruments, copies or transcriptions certified after verification as being accurate and complete, microfiches, photographic negatives, microfilm or magnetic media, x-rays, subject files, and records kept at the pharmacy, at the laboratories, and at medico-technical departments involved in the clinical trial.

8.3 Case Report Forms

The study case report form (CRF) is the primary data collection instrument for the study. All data requested on the CRF must be recorded. All missing data must be explained. If a space on the CRF is left blank because the procedure was not done or the question was not asked, write "N/D". If the item is not applicable to the individual case, write "N/A". All entries should be printed legibly in black ink. If any entry error has been made, to correct such an error, draw a single straight line through the incorrect entry and enter the correct data above it. All such changes must be initialed and dated. DO NOT ERASE OR WHITE OUT ERRORS. For clarification of illegible or uncertain entries, print the clarification above the item, then initial and date it.

8.4 Records Retention

It is the investigator's responsibility to retain study essential documents for at least 2 years after the last approval of a marketing application in their country and until there are no pending or contemplated marketing applications in their country or at least 2 years have elapsed since the formal discontinuation of clinical development of the investigational product. These documents should be retained for a longer period if required by an agreement with the sponsor. In such an instance, it is the responsibility of the sponsor to inform the investigator/institution as to when these documents no longer need to be retained.

9.0 STUDY MONITORING, AUDITING, AND INSPECTING

9.1 Study Monitoring Plan

The investigator will allocate adequate time for monitoring activities. The Investigator will also ensure that the medical monitor or other compliance or quality assurance reviewer is given access to all the above noted study-related documents and study related facilities (e.g. pharmacy, diagnostic laboratory, etc.), and has adequate space to conduct the monitoring visit.

9.2 Auditing and Inspecting

The investigator will permit study-related monitoring, audits, and inspections by the IRB, the funding sponsor, government regulatory bodies, and University compliance and quality assurance groups of all study related documents (e.g. source documents, regulatory documents, data collection instruments, study data etc.). The investigator will ensure the capability for inspections of applicable study-related facilities (e.g. pharmacy, diagnostic laboratory, etc.).

Participation as an investigator in this study implies acceptance of potential inspection by government regulatory authorities and applicable University compliance and quality assurance offices.

9.2.1 Independent External and Internal Audits

In addition to review by the DSMC, all studies initiated by SKCC investigators are audited by an independent auditor once they have achieved 10% of target accrual. However, a study can be audited at any time based on recommendations by the IRB, DSMC, PRC and/or the Director of Clinical Investigations, SKCC. Studies are re-audited once they have achieved 50% of target accrual. Special audits may be recommended by the IRB, DSMC or PRC based on prior findings, allegations of scientific misconduct and where significant irregularities are found through quality control procedures. Any irregularities identified as part of this process would result in a full audit of that study.

In addition to the audits at 10 and 50%, the CTO randomly audits at least 10 percent of all patients entered into therapeutic SKCC trials and other trials as necessary, on at least a bi-annual basis, to verify that there is a signed and dated patient consent form, the patient has met the eligibility criteria, and that SAEs are documented and reported to the TJU IRB.

All audit reports are submitted to the DSMC for review and action (when appropriate). A copy of this report and recommended DSMC action is sent to the PRC and TJU IRB. The committee regards the scientific review process as

dynamic and constructive rather than punitive. The review process is designed to assist Principal Investigators in ensuring the safety of study subjects and the adequacy and accuracy of any data generated. The TJU IRB may, based on the DSMC and auditor's recommendation, suspend or terminate the trial.

10.0 ETHICAL CONSIDERATIONS

This study is to be conducted according to US and international standards of Good Clinical Practice (FDA Title 21 part 312 and International Conference on Harmonization guidelines), applicable government regulations and Institutional research policies and procedures.

This protocol and any amendments will be submitted to a properly constituted independent Institutional Review Board (IRB), in agreement with local legal prescriptions, for formal approval of the study conduct. The decision of the IRB concerning the conduct of the study will be made in writing to the investigator before commencement of this study.

All subjects for this study will be provided a consent form that is compliant with local and federal regulations, describing this study and providing sufficient information for subjects to make an informed decision about their participation in this study. See Attachment for a copy of the Subject Informed Consent Form. This consent form will be submitted with the protocol for review and approval by the IRB for the study. The formal consent of a subject, using the IRB-approved consent form, must be obtained before that subject is submitted to any study procedure. This consent form must be signed by the subject or legally acceptable surrogate, and the investigator-designated research professional obtaining the consent.

11.0 STUDY FINANCES

11.1 Funding Source

This study is unfunded.

11.2 Conflict of Interest

Any investigator who has a conflict of interest with this study (patent ownership, royalties, or financial gain greater than the minimum allowable by their institution, etc.) must have the conflict reviewed by a properly constituted Conflict of Interest Committee with a Committee-sanctioned conflict management plan that has been reviewed and approved by the study sponsor prior to participation in this study. All Jefferson University Investigators will follow the TJU Conflicts of Interest Policy for Employees (107.03).

12.0 PUBLICATION PLAN

All investigators involved in the portion of the trial being published will review manuscripts prior to publication. The Principal Investigator will be ultimately responsible for the content of all manuscripts.

14.0 APPENDICES

Appendix I: Karnofsky Performance Scale

Able to carry on normal activity and to work; no special care needed.	100	Normal no complaints; no evidence of disease.
	90	Able to carry on normal activity; minor signs or symptoms of disease.
	80	Normal activity with effort; some signs or symptoms of disease.
Unable to work; able to live at home and care for most personal needs; varying amount of assistance needed.	70	Cares for self; unable to carry on normal activity or to do active work.
	60	Requires occasional assistance, but is able to care for most of his personal needs.
	50	Requires considerable assistance and frequent medical care.
Unable to care for self; requires equivalent of institutional or hospital care; disease may be progressing rapidly.	40	Disabled; requires special care and assistance.
	30	Severely disabled; hospital admission is indicated although death not imminent.
	20	Very sick; hospital admission necessary; active supportive treatment necessary.
	10	Moribund; fatal processes progressing rapidly.
	0	Dead

Appendix II. Case Report Forms

Version 6.0 (2017-10-16)

TELEPORT Study Case Report Form (CRF)—Screening Visit

Date of Screening: _____

Patient Demographics

Age: _____ Race: _____

Current Email Address: _____

Marital Status: _____

Highest Education Level Completed: _____

Karnofsky Performance Status:

Please assess the patient's performance status based on the table provided. Circle the most appropriate functional capacity.

Able to carry on normal activity and to work; no special care needed.	100	Normal no complaints; no evidence of disease.
	90	Able to carry on normal activity; minor signs or symptoms of disease.
	80	Normal activity with effort; some signs or symptoms of disease.
Unable to work; able to live at home and care for most personal needs; varying amount of assistance needed.	70	Cares for self; unable to carry on normal activity or to do active work.
	60	Requires occasional assistance, but is able to care for most of his personal needs.
	50	Requires considerable assistance and frequent medical care.
Unable to care for self; requires equivalent of institutional or hospital care; disease may be progressing rapidly.	40	Disabled; requires special care and assistance.
	30	Severely disabled; hospital admission is indicated although death not imminent.
	20	Very sick; hospital admission necessary; active supportive treatment necessary.
	10	Moribund; fatal processes progressing rapidly.
	0	Dead

TELEPORT Inclusion/Exclusion Criteria Checklist

Inclusion Criteria:

Patients must meet all of the following criteria in order to be considered for entry into the TELEPORT trial.

7. Patients who underwent, currently undergoing or planned to start radiation treatment in the next month with curative, adjuvant or palliative intent who have not yet had their first post-treatment visit
 - Age \geq 18
 - Karnofsky performance status at least 60%
 - Able to read and speak English and provide study specific informed consent prior to study entry
 - Have access to a computer or smartphone and internet connection at home on which they would be willing to do a telehealth study
 - Pennsylvania or New Jersey residents*

***Telehealth visits for New Jersey residents will only be performed by physicians with a current medical license issued by the state of New Jersey:**

[name]*

[name] MD PhD*

[name] MD*

[name] MD*

[name] MD*

[name] MD*

Exclusion Criteria:

In addition to meeting inclusion criteria, patients are ineligible for enrollment if any of the following exclusion criteria are met.

- Patients under the age of 18
- KPS <60%
- No access to a computer, smartphone or internet
- Unable to read and/or speak English
- Decisionally impaired patients
- Patients not residing in Pennsylvania or New Jersey

Checklist for Screening Visit:

Informed Consent for Trial Obtained	
All Sections of CRF Completed	
Inclusion/Exclusion Criteria Evaluated	
Based on screening patient appears eligible	

TELEPORT Study Case Report Form (CRF)—Follow up Visit
Patient Satisfaction with Cancer Care Scale (PSCC)

Below is a list of statements regarding your recent post-treatment visit. Please indicate your response

	Strongly agree (1)	Agree (2)	Neutral (3)	Disagree (4)	Strongly disagree (5)
I felt my concerns were understood					
I felt I was treated with courtesy and respect					
I felt included in decisions about my health					
I was told how to take care of myself					
I felt encourages to talk about my personal health concerns					
I felt I had enough time with my doctor					
My questions were answered to my satisfaction					
Making an appointment was easy					
I knew what the next step in my care would be					
I feel confident in how I deal with the health care system					
I was able to get the advice I needed about my health issues					
I knew who to contact when I had a question					
I received all the services I needed					
I am satisfied with the care I received					
The doctors seemed to communicate well about my care					
I received high quality care from my regular doctor					
I received high quality care from my specialists					
My regular doctor was informed about the results of the tests I got					

Communication assessment tool (CAT)

Please use this scale to rate the way the doctor communicated with you.

	Poor (1)	Fair (2)	Good (3)	Very good (4)	Excellent (5)
Greeted me in a way that made me feel comfortable					
Treated me with respect					
Showed interest in my ideas about my health					
Understood my main health concerns					
Paid attention to me(looked at me, listened carefully)					
Let me talk without interruptions					
Gave me as much information as I wanted					
Talked in terms I could understand					
Checked to be sure I understood everything					
Encouraged me to ask questions					
Involved me in decisions as much as I wanted					
Discussed next steps, including any follow up plans					
Showed care and concern					
Spent the right amount of time with me					

Health care system distrust scale

The next questions are about your opinion of the health care system in general. When we refer to the health care system, we mean hospitals, health insurance companies, and medical research. For each statement below, please indicate how strongly you agree or disagree

	Strongly agree (5)	Agree (4)	Not sure (3)	Disagree (2)	Strongly disagree (1)
Medical experiments can be done to me without my knowing about it					
My medical records are kept private					
People die every day because of mistakes by the health care system					
When they take my blood, they do tests they don't tell me about					
If a mistake were made in my health care, the health care system would try to hide it from me					
People can get access to my medical records without my approval					
The health care system cares more about holding costs down than it does about doing what is needed for my health					
I receive high-quality medical care from the health care system					
The health care system puts my medical needs above all other considerations when treating my medical problems					
Some medicines have things in them that they don't tell you about					

Physician questionnaire

	Yes	No	Not applicable
Were you able to assess the patient's symptoms?			
Were you comfortable assessing treatment related toxicity?			
Was a medication assessment done?			
Was KPS assessed and documented?			
If this was a telehealth visit, did you feel the need to bring the patient in to the office for further evaluation?			
Was patient provided with follow up instructions at the end of the visit?			
Was patient asked about follow up with other providers?			
Was patient provided with follow up labs and/or imaging instructions? Yes			
How long did today's visit take?	Today's visit took approximately _____ minutes		

Modified physician satisfaction scale

	Strongly agree (5)	Agree (4)	Not sure (3)	Disagree (2)	Strongly disagree (1)
I was able adequately to review this patient's laboratory results					
I was able adequately to review this patient's imaging					
I was able to elicit an adequate history from this patient					
I was able to communicate facts adequately to this patient					
I think this patient was satisfied with this clinical encounter					
My ability to evaluate this patient was significantly hampered because s/he was seen via televideo rather than in person					
It was as easy to ask intimate questions today as it would have been in person					
In general, I found the televideo system frustrating to use					
Compared with an in-person clinical encounter, I felt less sure that I was getting all of the information I needed					
I would like to use the televideo system again
